#### Secondary:

- Number of patients with polyps in the two arms
- Polyp number and size in relation to level of compliance to treatment.
- Risk stratification of polyps identified at follow up in each arm.
- Number of polyps with low, medium and high degree of dysplasia and cancer.
- Compliance, side effects and acceptability of treatment.
- User preference of carrot intake across patient profiles and carrot products.

# **Project description**

### WP1. Px7 Clinical trial (Lead: OUH. Partners: KUH, UUH, UMU, DR, NF, OF)

# Task1.1 Cultivation and quality control of carrots and juice production(Lead: OUH. Partners: DR, NF, OF)

DR will ensure timely production of the necessary amounts of "Yellowstone" carrots. The carrots will subsequently be transported to OF and NF, for production of both the carrot and the placebo juice. The final products will be shipped to the included centers 4 times a year. Other preparatory activities will also be handled in this task.

### Task1.2 Quantification of FaOH and FaDOH in the carrot and placebo juice. (Lead:OUH)

Both the carrot and the placebo juices will continuously be analyzed for FaOH/FaDOH contents throughout the study period. Any significant change in the concentration will be compensated.

### Task1.3 Preparation of the clinical trial (Lead: OUH. Partners: KUH, UUH, SUH)

The necessary preparations for the clinical trial will be undertaken. This includes obtaining the necessary regulatory and ethical approvals in both Denmark and Sweden, establishing an electronic Case Report Form (eCRF) using the REDCap software, writing trial instructions for staff, developing patient information material and consent forms, creating a randomization system with country stratification, and organize logistics. Finally, we will conduct dry-runs to test the functionality of all the different parts of the study.

- A database will be constructed in RedCap OPEN.
- Instructions for staff will be implemented.
- Approval from ethics committees and data protection agencies in Denmark and Sweden.
- Patient information and consent forms.
- Randomization systems with country stratification
- Dry runs will be performed to test logistics and patient flow.

### Task1.4 Clinical trial (Lead: OUH. Partners: KUH, UUH, SUH)

We will conduct a prospective double-blinded randomized controlled trial in 1 Danish and 3 Swedish centers. Participants in the intervention arm will receive a daily treatment with 100mL FaOH/FaDOH-rich carrot juice for 1 year. Participants in the placebo arm will receive a daily treatment with 100 mL of placebo juice for 1 year. We will include patients who undergo a resection of high-risk colorectal adenomas, who meets the inclusion criteria at the time of their procedure.

# WP 2 – Patient compliance (Lead: OUH and UMU)

# Task 2.1 – compliance (Lead: OUH and UMU)

Through a close collaboration OUH and UMU will look at ways to keep compliance up for participant.

### Task 2.2 – Carrots (Lead: OUH and UMU)

UMU will look at different ways of how to use carrots and also how to make the juice more delicious if there is other ways we can implement carrot in our daily routines.

# Methodology

# Design of the intervention

The trial will be conducted as a double-blind controlled, randomized study. Patients, who, at colonoscopy, had high-risk adenomas, are randomized in 2 arms. One arm will receive 100 ml of carrot juice with a high concentration of falcarinol and falcarindiol daily for 1 year and the other arm will receive 100 ml of placebo juice daily for 1 year until their follow up full colonoscopy. The placebo juice will be produced from commercially available artificial juice without Falcarinol or Falcarindiol. At the follow up colonoscopy, another standardized report will be fulfilled by the endoscoper, containing information about recurrence, the number of polyps, polyp size and risk stratification (no-, low-, medium, high risk polyps or cancer).

The compliance will be registered through diaries/calendars and patients will be followed through the entire period, regardless of their level of compliance. Patients with compliance drop-outs will be encouraged to reenter and complete with as high a compliance as possible.

Patients will be informed that they will receive a call after 1 month from each appointment, where their questions and concerns will be answered.

After the first colonoscopy, patients will be offered inclusion into the trial. If the resection of the high-risk polyp took place in the first colonoscopy, the patient will call the project nurse if he/she is interested in participating in the study and make an appointment for being enrolled in the project. If the resection will take place in a specialized unit where a second colonoscopy will be performed for the resection, then they will give their final answer at this appointment.

The patient will collect 8 liters of juice/placebo every 2 months at a visit at the clinic. At this visit, they will be interviewed for compliance, intake of additional carrots/carrot containing products and possible side effects. If the project nurse assesses the patient as non-compliant then he/she will be excluded from the study.

Each participant will have 6 visits and the 4 institutions will in total have 2400 visits, which is approximately 600 visits in two years at each institution. Visits can be organized in weekly group sessions. Compliance diaries and questionnaires will be explained and collected according to written instructions.

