### Secondary aim:

Compliance and side effects will be registered through questionnaire and diary and we will identify critical pathways in patient acceptability and compliance of carrot intake from a diary.

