# **Common pathway**

At the inclusion visit, a compliance diary/calendar will be handed out for registration of compliance and also a basic questionnaire. Patients will be given 2 months juice (8 liters) when included and will be appointed after 2 months to collect another 8 liters of juice in the department. Patients will be informed that they will receive a call after 1 month from each appointment, where their questions and concerns are answered. If the patients need to reschedule the appointment he/she can call at the number that will be written on the information paper or if he/she doesn't show up, the dedicated staff will contact them on the number they wrote in the questionnaire.

Regarding of the recruitment scenario (1 or 2), in order to follow the national guidelines, patients who have had a piecemeal resection will have an additional control colonoscopy at 3 months.

All patients will undergo a full colonoscopy at one year from the moment of the enrollement After the procedure, information about recurrence, the number of polyps, polyp size and characterization will be registered in the database. Polyp size will be measured with the aid of appropriate instruments, like biopsy forceps and slings.

After completing the study period of 1 year, all patients will enter the standard follow up program.

[figure not shown]
Full compliance is defined as consumption of > 75% of the juice delivered. However, because we do not know the minimal effective dose, all participants will be encouraged to continue the study even if they had drop-outs of juice consumption that lead to a < 75% compliance. In addition, participants with incomplete compliance will be registered and included in the study as a sub-group for separate analysis. But the project nurse will assess the patients every 2 months when they pick up the juice and if almost complete non-compliance is registered, the patient will be excluded from the study.

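### Compliance is defined by volume but measured only by self-report, although leftover juice could be measured at the 2-monthly collection visits; the 75% cut-off also sits almost on top of perfect intake

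*Protocol*

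**What the plan says.** **Instruments.** Under Secondary aim: "Compliance and side effects will be registered through questionnaire and diary". Under Design of the intervention: "The compliance will be registered through diaries/calendars", and of the 2-monthly visit it says: "At this visit, they will be interviewed for compliance, intake of additional carrots/carrot containing products and possible side effects". All of these depend on what the patient reports.

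**Definition.** Under Common pathway: "Full compliance is defined as consumption of > 75% of the juice delivered". The same section says that participants with incomplete compliance form a sub-group to be analysed separately.

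**Delivered volume and visits.** "The patient will collect 8 liters of juice/placebo every 2 months at a visit at the clinic", and "Each participant will have 6 visits and the 4 institutions will in total have 2400 visits". The planned intake in both arms is 100 ml a day for one year.

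**Uses of the measure.** Compliance is a secondary outcome in its own right. A second one is "Polyp number and size in relation to level of compliance to treatment". It also enters a decision on participation: "If the project nurse assesses the patient as non-compliant then he/she will be excluded from the study".

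**What is absent.** No section shown asks patients to bring back unused juice, or staff to record it. The serum falcarinol assay appears in the Background and is not assigned to compliance. The samples taken from participants' homes (Product section) test the content of the juice, not intake.

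**The concern.** The definition is a ratio of two volumes. The denominator is known exactly because the clinic hands it out. The numerator rests on recall and candour alone, although the patient is back in the clinic every 2 months and is already being asked about compliance.

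If some patients report more than they drank, true non-compliers are counted as compliers. The two compliance groups then look more alike than they are, which weakens any relation between intake and polyps and thins out the sub-group of incomplete compliers. Leftover volume that is not recorded at the visit cannot be recovered by later analysis, so this is a matter of data collection and not one to leave to a statistical analysis plan.

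The size of the reporting error that matters depends on how far typical patients lie from the 75% cut-off, so that distance needs checking too.

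**Working it through.** The plan gives no figure for the accuracy of the compliance measure, so there is none to reproduce. The visit count is internally consistent: 400 × 6 = 2400, and 2400 / 4 = 600 per institution.

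**Step 1. Where perfect intake lies relative to the cut-off.** Inputs: 8 L every 2 months, six deliveries, 100 ml a day for a year, and a cut-off of more than 75% of delivered.

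- Delivered: 6 × 8 L = 48 L.
- Planned intake: 365 × 0.1 L = 36.5 L.
- Perfect intake as a share of delivered: 36.5 / 48 = 76.0%.
- Cut-off: 0.75 × 48 L = 36 L, which is 360 daily portions, or 36 / 36.5 = 98.6% of planned intake.
- Margin: 365 − 360 = 5 days. Five missed days give exactly 75.0%, which is not above 75%.

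The result is the same for one interval, with its length assumed:

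| Days between visits | Perfect intake | Share of 8 L |
|---|---|---|
| 59 | 5.9 L | 73.75% |
| 60 | 6.0 L | 75.0% |
| 61 | 6.1 L | 76.25% |
| 62 | 6.2 L | 77.5% |

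Judged interval by interval, a patient who misses nothing would fail the definition after 60 days or fewer.

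**Step 2. What should be left over.** Over 61 days: 8 − 6.1 = 1.9 L. Over the year: 48 − 36.5 = 11.5 L. Every patient, including a perfect complier, should have juice to show, so a measured leftover says something about everyone.

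**Step 3. Illustrated effect of over-reporting.** Inputs:

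- True compliers: 80%. The Abstract expects this share to comply through the year. Applying it to the >75% definition is an assumption.
- Polyp rates: 20% in compliers and 40% in non-compliers (assumed).
- Fraction f of non-compliers who report full compliance: 0.25, 0.50 or 0.75 (assumed).
- No complier under-reports, and misreporting is unrelated to polyp status (assumed).

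Observed rate among reported compliers = (0.80 × 0.20 + 0.20f × 0.40) / (0.80 + 0.20f).

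| f | Observed rate in reported compliers | Difference from 40% | Attenuation of 20 points |
|---|---|---|---|
| 0.25 | 0.18 / 0.85 = 21.2% | 18.8 points | 5.9% |
| 0.50 | 0.20 / 0.90 = 22.2% | 17.8 points | 11.1% |
| 0.75 | 0.22 / 0.95 = 23.2% | 16.8 points | 15.8% |

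The relative attenuation equals 1 − 0.80 / (0.80 + 0.20f). It therefore depends on the share of compliers and on f, not on the two polyp rates.

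**Step 4. Would a simple container count do?** Container size is not stated; assume 1 L. After 61 days of perfect intake the patient has one unopened and one part-used container. Counting both as returned gives (8 − 2) / 8 = 75.0%, so a perfect complier is classed as incomplete. The leftover has to be recorded as a volume.

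**The case against.** **The diary can give a volume.** With a fixed 100 ml portion, days taken × 100 ml is consumption, and no leftover is needed to compute the ratio. This stands. The weakness is that the figure is self-reported, not that it cannot be formed.

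**Patients are not clearly pushed to over-report.** A reader might infer from the nurse's power to exclude that there is a built-in incentive to overstate intake. The documents do not support that as a firm claim. Design of the intervention says patients are followed whatever their compliance and are encouraged to re-enter. Common pathway encourages those below 75% to continue and limits exclusion to almost complete non-compliance. Nothing shown says patients are told that low reported intake leads to exclusion. The tension between these passages is a separate matter.

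**Returned juice is not a gold standard.** Juice that is poured away or shared counts as drunk, an error in the same direction as over-reporting. This stands, and with Step 4 it is why the measured leftover should sit beside the diary and not replace it. The two sources do not fail for the same reasons, so disagreement between them is informative.

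**A return procedure may exist elsewhere.** The patient-flow attachment, a figure and the written instructions for staff are not shown, so this cannot be ruled out. If there is one, the two protocol sections should refer to it.

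**Conclusion.** The point holds as a measurement weakness in a secondary outcome and a sub-group. It is not a contradiction or an error in the plan. Compliance is defined by volume, the sections shown measure it by self-report alone, and a second measure is available at visits already planned.

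The firmest part is arithmetical. If six deliveries of 8 L are made, perfect intake is 76% of delivered, and five missed days in a year reach the 75% limit. Small reporting errors can therefore change a patient's classification.

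The attenuation of about 6 to 16% is an illustration. It rests on the protocol's 80% and on assumed polyp rates and misreporting fractions. A reader who assumes only 70% compliers would obtain 10 to 24%, but the protocol gives no basis for that lower share.

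Nor should it be inferred that the main result is at risk. The randomised comparison of everyone followed up does not use the compliance measure.

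**What to change.** 1. In Design of the intervention and Common pathway, ask patients to bring unused and part-used juice to each collection visit. Record the leftover volume in the eCRF, not just the number of containers. If the six collections start at inclusion, the last delivery has no later collection visit, so name the occasion, such as the one-year colonoscopy, at which its leftover is recorded. Note whether the patient keeps the leftover, so that it is not counted twice.
2. Keep the diary, and use delivered minus leftover as a second measure. Repeat the compliance sub-group analysis and the secondary outcome on polyps by compliance level with the volume-based measure, as a sensitivity analysis.
3. Reconcile the volumes behind the cut-off. The 48 L delivered and the 36.5 L planned make a limit expressed as a share of delivered almost the same as perfect intake. State which volume the percentage refers to, over what period it is assessed, and how the diary is turned into a volume.

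**Cost.** No extra visit is needed. Patients carry leftovers back, and staff spend a few minutes measuring at each visit, which adds up over 2400 visits and needs some organisation if visits are run as group sessions. Discarded juice will still be counted as drunk. Item 3 needs only a change of text.

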#### **Deviation from standard treatment**

The time from adenoma resection to follow-up colonoscopy in case of high-risk adenomas was in Denmark 1 year and for piecemeal resection for 3 months control colonoscopy and after 12 months for full colonoscopy. This has been changed per May 1, 2023 to: for piecemeal resection-at 6 months a control colonoscopy and afterwards a full colonoscopy at 18 months and for en-bloc resection a full colonoscopy at 18 months. In Sweden, the period is 1-3 years depending on the type of high-risk adenomas. In this study piecemeal resection patients are invited at a 3 month control colonoscopy and they are all invited for full colonoscopy after one

year. This means that patients will have an earlier follow up. This regimen is compliant with international guidelines in many European countries.

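### The protocol both follows and excludes non-compliant randomised patients, so their one-year outcome may be lost and the comparison biased

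*Protocol*

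**What the plan says.** The protocol gives several rules for patients who do not drink the juice.

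- *Design of the intervention*, on follow-up: "patients will be followed through the entire period, regardless of their level of compliance".
- The same section, on the two-monthly visits: "If the project nurse assesses the patient as non-compliant then he/she will be excluded from the study". No threshold for non-compliance is given.
- *Common pathway* defines full compliance as more than 75% of the juice delivered, then says that "all participants will be encouraged to continue the study even if they had drop-outs of juice consumption that lead to a < 75% compliance", and that "participants with incomplete compliance will be registered and included in the study as a sub-group for separate analysis".
- The same paragraph ends: "if almost complete non-compliance is registered, the patient will be excluded from the study". No figure says how little juice this means.

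Two other places need outcome data from these patients. *Common pathway* states: "All patients will undergo a full colonoscopy at one year from the moment of the enrollement". The secondary outcomes include "Polyp number and size in relation to level of compliance to treatment".

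*Deviation from standard treatment* shows what happens outside the trial. Since May 2023 the Danish routine has been "for en-bloc resection a full colonoscopy at 18 months", and the full colonoscopy after piecemeal resection is also at 18 months. The Swedish interval is 1-3 years.

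**The concern.** The instructions cannot all be carried out. A patient cannot be followed whatever the compliance and also be removed for poor compliance. The two sections also set different thresholds for removal, so a site working from one would exclude different patients from a site working from the other.

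The exclusion is made after randomisation, at juice pick-up, by staff judgement. It can depend on how the allocated juice tastes or is tolerated. If the share excluded, or the recurrence risk of those excluded, differs between arms, the remaining groups are no longer the randomised ones.

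The harm may be permanent. The primary outcome is read at a trial-specific one-year colonoscopy. A patient who leaves the study for routine care may not have one, and no analysis plan can recover an examination that was not done.

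**Working it through.** **Rules side by side**

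| Patient | *Design of the intervention* | *Common pathway* |
|---|---|---|
| Below 75%, still drinking some juice | Followed; but excluded if the nurse judges non-compliant | Kept, analysed as a sub-group |
| Almost no juice | Followed; but excluded if the nurse judges non-compliant | Excluded; yet all patients have the one-year colonoscopy |

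The conflict lies within the first section, within the second for near-zero takers, and between the two on the threshold. Neither section says whether exclusion means stopping juice only or also ending outcome collection.

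**How large could the bias be?** The protocol gives no figure to reproduce: it states no exclusion share by arm and no recurrence risk in non-compliers. What follows is an illustration on the proportion of patients with recurrence, the quantity used in *Sample size*.

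Inputs from the protocol: 40% recurrence; 400 patients in two equal arms, so 200 each; planned effect 20 percentage points. Assumed: no true effect; two-sided 5% level (not stated in the protocol); share excluded *s*; recurrence risk among the excluded *q*.

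- Rate among those remaining = (0.40 − s·q)/(1 − s)
- Remaining patients with recurrence = 200·(0.40 − s·q)
- Type I error = Φ(−1.96 + d/SE) + Φ(−1.96 − d/SE), where d is the false difference and SE = √[p₁(1−p₁)/n₁ + p₂(1−p₂)/n₂]

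Example, s = 0.20 active and 0.10 placebo, q = 0.6:

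- Active: (0.40 − 0.12)/0.80 = 0.28/0.80 = 35.0% of 160.
- Placebo: (0.40 − 0.06)/0.90 = 0.34/0.90 = 37.8% of 180.
- d = 2.8 points, SE = 5.2 points, type I error 8.3%.

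| Excluded, active / placebo | Risk in excluded | Remaining rate, active vs placebo | False difference, points | Type I error |
|---|---|---|---|---|
| 20% / 10% | 50% | 37.5% vs 38.9% | 1.4 benefit | 5.8% |
| 20% / 10% | 60% | 35.0% vs 37.8% | 2.8 benefit | 8.3% |
| 20% / 10% | 30% | 42.5% vs 41.1% | 1.4 harm | 5.8% |
| 20% / 10% | 40% (average) | 40% vs 40% | 0 | 5.0% |
| 5% / 2.5% | 50% | 39.5% vs 39.7% | 0.3 benefit | 5.03% |
| 5% / 2.5% | 60% | 38.9% vs 39.5% | 0.5 benefit | 5.13% |
| 20% / 5% | 60% | 35.0% vs 38.9% | 3.9 benefit | about 12% |
| 20% / 20% | 60% active, 40% placebo | 35.0% vs 40.0% | 5.0 benefit | about 15% |
| equal shares | equal risk | equal | 0 | 5.0% |

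**Totals.** *Aim* words the primary endpoint as the total number of recurrent adenomas in an arm times their mean size. A total also falls simply because patients are removed. With 20% versus 10% excluded, patients with recurrence number 60 vs 70 (q = 0.5; 60/70 = 0.857, 14% fewer) or 56 vs 68 (q = 0.6; 56/68 = 0.824, 18% fewer). Most of this is a denominator effect: at average risk the counts are 64 vs 72, already 11% fewer with no selection at all.

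**The case against.** The strongest reply is that *Common pathway* is the detailed compliance text, and that the sentence under *Design of the intervention* is shorthand for it. On that reading only near-zero takers are removed. The 5% versus 2.5% case is then nearer the mark than 20% versus 10%, and its bias is 0.3-0.5 points with a type I error that is practically nominal. The trial is double-blind and, according to *Product - carrot juice and placebo*, taste is adjusted so that the juices cannot be told apart, which argues against a large imbalance. The illustration uses the proportion with recurrence, whereas the primary outcome is number and size. The loss of the one-year colonoscopy is inferred: the protocol says that all patients have it, and some Swedish patients would have one at about a year in routine care. Finally, analysis populations are commonly left to the analysis plan.

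Much of this stands as a limit on size. The bias may be small, its direction is unknown, and the type I error figures do not describe the number-times-size endpoint. It does not remove the contradiction: on the narrow reading near-zero takers are still both followed and excluded, and no text says that their outcome is collected. Nor can the point be left wholly to the analysis plan, because whether the examination is sought is a conduct rule that the protocol itself states inconsistently.

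**Conclusion.** The concern holds, and the text must be fixed. The protocol gives incompatible instructions on whether non-compliant randomised patients stay under follow-up, sets two different unquantified thresholds for removing them, and does not secure their one-year outcome.

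The size of any bias cannot be derived from the documents. In the illustrations it runs from zero to about 5 points, against a planned effect of 20, and it can go either way. It is zero when equal shares of similar patients are removed or when the excluded carry average risk. These figures rest on assumed exclusion shares and risks and on a 5% level. The conclusion does not depend on any one of them: it rests on the contradictory wording and on the fact that a missed examination cannot be replaced later.

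**What to change.** Reconcile *Design of the intervention* and *Common pathway* so that neither non-compliance nor stopping juice ends outcome follow-up, and say what exclusion means if the word is kept. State that the one-year colonoscopy is sought from every randomised patient who has not withdrawn consent, and that the primary comparison is by allocated arm irrespective of compliance. Keep the secondary outcome on compliance and the incomplete-compliance sub-group as supportive analyses. The handling of colonoscopies that are still missing can go in the analysis plan. None of this takes a position on whether a patient should continue the juice.

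The cost is protocol wording and the effort of bringing non-compliers to the one-year examination. For many it is earlier than routine, but it is already planned for all patients.

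There is also some dilution. If 20% of the active arm took no juice and kept a 40% risk while the rest had 20%, the active rate would be 0.8 × 20% + 0.2 × 40% = 24%. Power for 40% versus 24% with 400 patients is 93%, compared with 98% for 40% versus 20% in 320 patients. That is a modest price for keeping the randomised comparison intact.
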